4.4.5.3 Delayed Treatment Effect

The weighted log-rank analysis ([Fleming and Harrington 1991](#)) that weights more on late events ([Fine et al. 2007](#)) will be conducted to assess a potential delayed treatment effect for the treatment group.

Statistical methodologies analogous to those used in the analysis of PFS or OS as specified in Section 4.4.1 and Section 4.4.2.4 will be used for these sensitivity analyses. The sensitivity analysis is based on the stratified analyses.

4.4.6 Subgroup Analyses

The consistency of the PFS and OS results will be examined in subgroups defined by demographic and baseline characteristics and stratification factors. Summaries of PFS and OS, including the unstratified HR estimated from a Cox proportional hazards model and Kaplan-Meier estimates of median PFS and OS, will be produced by treatment arm for each of the defined subgroups, and displayed in a Forest plot ([Lewis and Clarke 2001](#)).

The subgroups to be considered include but are not limited to the following:

- Age (≤ 65 years, > 65 years) at randomization
- Race (non-White, White)
- Sex (female, male)
- Geographic Region (North America, Europe, Australia/New Zealand/Others)

- LDH (\leq ULN, $>$ ULN)
- Eastern Cooperative Oncology Group (ECOG) performance status (0, 1)
- Melanoma staging
- PD-L1 expression

4.5 SAFETY ANALYSES

Safety analyses will be performed on the safety population and will include all randomized patients who received any amount of any study drug, with patients grouped as follows:

- Atezolizumab+cobimetinib+vemurafenib arm: patients who received any amount of atezolizumab with or without any amount of cobimetinib or vemurafenib
- Placebo+cobimetinib+vemurafenib arm: patients who received any amount of cobimetinib or vemurafenib without any amount of atezolizumab

4.5.1 Exposure of Study Medication

Study drug exposure, including treatment duration, number of doses, and dose intensity will be summarized for each treatment arm using descriptive statistics.

4.5.2 Adverse Events

Verbatim description of AEs will be mapped to Medical Dictionary for Regulatory Activities (MedDRA) thesaurus levels and graded according to NCI CTCAE v4.0. All AEs that occur during or after the first study drug dose will be summarized by treatment arm and NCI CTCAE grade. In addition, serious adverse events (SAEs), AEs (Grade 3–5), [REDACTED] and AEs leading to study drug discontinuation or interruption will be summarized accordingly. AEs leading to dose reduction will be summarized for cobimetinib and vemurafenib.

Multiple occurrences of the same event will be counted once at the maximum severity. The proportion of patients who experience at least one AE will be reported by toxicity term and treatment arm.

All deaths and causes of death will be summarized.

Listings of AEs will include all AEs with an onset that occurred on or after the first study drug treatment up to the data cutoff date.

In addition, deaths, SAEs, [REDACTED], and AEs (Grade 3–5) during the study run-in period, will be summarized. To evaluate safety during triple combination period (i.e., post run-in), SAEs, AEs (Grade 3–5), and AE leading to any study drug discontinuation will be summarized.

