5.3.1 Adverse Event Reporting Period

Investigators will seek information on adverse events at each patient contact. All adverse events, whether reported by the patient or noted by study personnel, will be recorded in the patient's medical record and on the Adverse Event eCRF.

After informed consent has been obtained **but prior to initiation of study treatment**, only serious adverse events caused by a protocol-mandated intervention (e.g., invasive procedures such as biopsies, discontinuation of medications) should be reported (see Section 5.4.2 for instructions for reporting serious adverse events).

After initiation of study treatment, adverse events will be reported as follows:

- All adverse events will be reported until 30 days after the final dose of study treatment or until initiation of subsequent anti-cancer therapy, whichever occurs first
- Serious adverse events and [REDACTED] will continue to be reported until 90 days after the final dose of study treatment or until initiation of subsequent anti-cancer therapy, whichever occurs first.
- All new primary neoplasms (benign or malignant), including new primary melanoma, will be reported until 6 months after the final dose of vemurafenib. Any new primary malignant neoplasm other than cutaneous squamous cell carcinoma should be reported as a serious adverse event.

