5.6 ADVERSE EVENTS THAT OCCUR AFTER THE ADVERSE EVENT REPORTING PERIOD

After the end of the adverse event reporting period for deaths (defined as 90 days after the final dose of study treatment), all deaths, regardless of cause, should be reported through use of the Long-Term Survival Follow-Up eCRF.

In addition, if the investigator becomes aware of a serious adverse event that is believed to be related to prior exposure to study treatment, the event should be reported through use of the Adverse Event eCRF. However, if the EDC system is not available, the investigator should report these events directly to the Sponsor or its designee, either by faxing or by scanning and emailing the Serious Adverse Event [REDACTED] Reporting Form using the fax number or email address provided to investigators.

5.7 EXPEDITED REPORTING TO HEALTH AUTHORITIES, INVESTIGATORS, INSTITUTIONAL REVIEW BOARDS, AND ETHICS COMMITTEES

The Sponsor will promptly evaluate all serious adverse events and [REDACTED] [REDACTED] against cumulative product experience to identify and expeditiously communicate possible new safety findings to investigators, IRBs, ECs, and applicable health authorities based on applicable legislation.

To determine reporting requirements for single adverse event cases, the Sponsor will assess the expectedness of these events using the following reference documents:

- Atezolizumab Investigator's Brochure
- Cobimetinib Investigator's Brochure
- Vemurafenib Investigator's Brochure

The Sponsor will compare the severity of each event and the cumulative event frequency reported for the study with the severity and frequency reported in the applicable reference document.

Reporting requirements will also be based on the investigator's assessment of causality and seriousness, with allowance for upgrading by the Sponsor as needed.

An iDMC will monitor the incidence of the above-listed anticipated events during the study. An aggregate report of any clinically relevant imbalances that do not favor the test product will be submitted to health authorities.

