All patients will be closely monitored for safety and tolerability throughout the study. The National Cancer Institute Common Toxicity Criteria for Adverse Events, Version 4.0 (NCI CTCAE v4.0) will be used to characterize the toxicity profile of the study treatments for all patients. Patients will be assessed for adverse events (AEs) according to the schedule of activities (see [Appendix 2](#)) and as necessary throughout the study.

Tumor assessments will be performed by the investigator and by an independent review committee (IRC) according to RECIST v1.1. Tumor assessments according to [REDACTED] will only be performed by the investigator. All measurable and non-measurable lesions will be documented at screening. Response will be assessed by the investigator at 8- or 12-week intervals until investigator-determined disease progression (according to RECIST v1.1), or death, whichever occurs first. Patients who experience disease progression (RECIST v1.1) must have scans following the

protocol-specified tumor assessment schedule after initial documentation of progression to confirm disease progression. Tumor assessments are to continue according to schedule in patients who discontinue treatment for reasons other than confirmed disease progression. Clinically stable patients who have a favorable benefit-risk ratio should continue on study treatment following radiographic progression per RECIST v1.1. Patients who continue treatment beyond radiographic disease progression will be closely monitored.

Study treatment will continue for all patients until investigator-determined disease progression according to RECIST v1.1 that is confirmed by repeat scans approximately 4-8 weeks later or subsequent clinical deterioration, unacceptable toxicity, death, patient or physician decision to withdraw, or pregnancy, whichever occurs first. Patients who discontinue one study drug may be able to continue other study drugs, per guidelines for management of specific AEs provided in the Protocol Section 5.1. After treatment discontinuation, patients will be followed for disease progression if applicable and followed for survival until death, withdrawal of consent, or loss to follow-up, whichever occurs first. Patients in the control arm cannot crossover to the treatment arm at disease progression. An independent Data Monitoring Committee (IDMC) will be employed to conduct periodic evaluations of safety data.

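### SAP 4.5.2 compares adverse events between arms only as crude proportions, which also move with time on drug; exposure-adjusted rates by period should stand beside them

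*SAP*

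**What the plan says.** The SAP's counting rule for the summary tables has a start and no stated end: "All AEs that occur during or after the first study drug dose will be summarized by treatment arm and NCI CTCAE grade". The measure is a proportion: "The proportion of patients who experience at least one AE will be reported by toxicity term and treatment arm". Each event is counted once, at its worst grade. The same section adds separate summaries for the run-in (deaths, serious events, Grade 3-5 events and a redacted category) and for the triple combination period (serious events, Grade 3-5 events, events leading to discontinuation of any drug). The data cutoff is mentioned only for the listings, which take "all AEs with an onset that occurred on or after the first study drug treatment up to the data cutoff date".

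Protocol 5.3.1 sets what is collected. The general rule is: "All adverse events will be reported until 30 days after the final dose of study treatment or until initiation of subsequent anti-cancer therapy", whichever is first. Serious events and a redacted category "will continue to be reported until 90 days after the final dose of study treatment or until initiation of subsequent anti-cancer therapy". New primary neoplasms "will be reported until 6 months after the final dose of vemurafenib". Beyond these windows, Protocol 5.6 asks for a report only "if the investigator becomes aware of a serious adverse event that is believed to be related to prior exposure to study treatment".

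SAP section 2 ties treatment length to the primary endpoint: "Study treatment will continue for all patients until investigator-determined disease progression according to RECIST v1.1", once confirmed by repeat scans, or until clinical deterioration, toxicity, death, withdrawal or pregnancy. SAP 4.5.1 describes exposure by arm, but no visible analysis uses it as a denominator for adverse events.

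**The concern.** The collection window closes a fixed interval after the last dose, so its length follows time on drug. A patient treated for longer has more time in which a first event can occur and be recorded. The primary hypothesis is that progression-free survival differs between arms. If it does, time on drug probably differs too, and a crude proportion then mixes a difference in risk with a difference in observation time. The planned exposure table lets a reader see an imbalance, but not how much of an adverse event difference it explains. At stake is the safety half of the benefit-risk comparison: an excess in one arm could be read as toxicity when part of it is longer observation, or a real excess could be hidden if the experimental arm stops earlier.

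**Working it through.** **Plan's own figure.** There is none. The adverse event sections give no rates, and the progression-free survival assumptions and analysis timing are redacted. What follows is illustration on stated assumptions.

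**Closed-form check.** Let time on drug be exponential with hazard m = ln 2 / median, let the event hazard h be constant and equal in both arms, let collection run w = 30 days (0.986 months) past the last dose, and apply no cutoff. Then

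crude proportion = 1 - exp(-h w) x m / (m + h).

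The medians are set at 11 and 14 months, the range of progression-free survival that Protocol 1.1 quotes for combined BRAF and MEK inhibition in other trials. Choose h so that Arm A shows 30%: h = 0.0248 per month and exp(-h w) = 0.976.

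- Arm A: m = 0.0630, m/(m+h) = 0.717, proportion = 1 - 0.976 x 0.717 = 30.0%.
- Arm B: m = 0.0495, m/(m+h) = 0.666, proportion = 1 - 0.976 x 0.666 = 35.0%.

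With a cutoff at 30 or 18 months, Arm B is 33.6% or 32.4%. At equal medians the gap is zero. With the medians reversed (A 14, B 11), Arm B shows 25.4% to 27.7% against 30%.

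**Fuller simulation.** Assumptions: median time on drug 10 months (A) and 14 months (B), median survival after treatment 12 months, next therapy 1 to 3 months after stopping, cutoff 12 to 30 months. Collection ends at the earliest of 30 days after the last dose, next therapy, death or cutoff. Crude incidence at equal hazards:

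- h = 0.01 per month: 10.7% vs 12.3%, gap 1.6 points
- h = 0.03 per month: 27.6% vs 31.4%, gap 3.8 points
- h = 0.06 per month: 45.4% vs 50.6%, gap 5.2 points

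First events per 100 patient-years at risk are the same in both arms (12, 36 and 72, that is 1200 x h), so the adjusted rate removes the artefact when the hazard is constant. All of this gap arises inside the 30-day window.

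**Early-onset events.** Keep the exposure assumptions, but let the common hazard be 0.10 per month for 3 months and 0.01 afterwards. Crude incidence is 30.9% vs 32.3%, a gap of only 1.4 points. A single overall adjusted rate is then about 43.8 (A) vs 39.9 (B) per 100 patient-years: Arm B looks safer although the hazards are identical. Split at month 3, the rates are about 120 vs 120 and then about 12 vs 12. The adjustment therefore has to be by period.

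**The case against.** Several points on the other side stand.

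- The tables are descriptive, with no test or decision rule. A crude proportion validly describes the burden of each regimen as given, and exposure is reported beside it.
- The run-in summary covers a nearly fixed window (28 days, extendable to 56) and is largely free of the problem. It ends before atezolizumab starts, however, and the post-run-in summary is neither fixed in length nor adjusted.
- Unequal exposure is an inference. Treatment can continue past radiographic progression, single drugs can stop while others continue, and toxicity may shorten treatment in either arm.
- Some relevant events come early. Protocol 5.1.3.1 describes cutaneous squamous cell carcinoma as usually early, and 5.1.3.14 places neutropenia mostly in the first 6 to 12 weeks. These move little with exposure.
- A single exposure-adjusted rate carries its own distortion, as shown above.

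Two stronger readings are tempting, and the documents support neither. A reader might infer that the missing end date, by pooling late, causality-filtered reports with routine ones, drives the difference. It does not: the quantified gap exists wholly within the 30-day window, so truncating the tables there would remove none of it. After 90 days only new neoplasms and serious events believed related can enter, and nothing in the documents indicates how many. A reader might also infer that the SAP tabulates every event up to data cutoff; that wording governs the listings, where full inclusion is appropriate.

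**Conclusion.** The point holds as a worthwhile and inexpensive addition. Every planned comparison of adverse events by arm is a crude proportion, collection time follows time on drug, and no visible analysis separates the two. The size of about 1.6 to 5.2 points rests on assumed medians of 10 and 14 months, constant and equal hazards, and the assumed follow-up pattern. It is zero at equal exposure, changes sign if Arm B stops earlier, and shrinks for early-onset events. It would be too strong to say that the comparison is biased against Arm B, because the documents give no expected exposure by arm. The absent end date for the summary tables is a minor wording point, separate from this gap.

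**What to change.** Keep the crude tables. Add to SAP 4.5.2, for serious events, Grade 3-5 events and events leading to discontinuation:

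1. First-event incidence per 100 patient-years at risk, by arm. Time at risk runs from first dose to the first event or the end of the Protocol 5.3.1 collection window for that event type, whichever is earlier, capped at death and data cutoff. If the redacted category is also given a rate, it should keep its 90-day window.
2. Rates split by period (run-in, first 3 months of triple combination, later), or time-to-first-event estimates instead, because one overall rate assumes a constant hazard.
3. A statement that serious events reported only under Protocol 5.6 are left out of these rates and kept in the listings.

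While editing, name the end of the window for the summary tables. The cost is SAP wording and a few extra outputs from dates the trial already collects; no data collection or patient management changes.

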4.5.3 Laboratory Data

Laboratory data will be summarized over time including change from baseline. Values outside the normal ranges will be summarized. Additionally, selected laboratory data will be classified in accordance with NCI CTCAE v4.0 and will be summarized by grade. Highest NCI CTCAE grade post-baseline will also be reported, and shift tables from baseline to worst value during the study post-baseline will be presented.

4.5.4 Vital Signs

Changes in selected vital signs will be summarized by treatment arm and by change over time including change from baseline.

4.6 PHARMACOKINETIC AND PHARMACODYNAMIC ANALYSES

PK samples of cobimetinib, vemurafenib, and atezolizumab concentration-time data will be overlaid with typical concentration-time profiles for each molecule using existing population PK models to determine if exposures in this study are consistent with previously characterized pharmacokinetics. In addition, individual patient PK parameters will be determined using the non-linear mixed-effects modeling. The results of PK analyses may be reported in a standalone report and may not be reported in the CSR.

4.7 IMMUNOGENICITY ANALYSES

The numbers and proportions of atezolizumab anti-drug antibody (ADA)-positive patients and ADA-negative patients at baseline (baseline prevalence) and after baseline (post-baseline incidence) will be summarized. When determining post-baseline incidence, patients are considered to be ADA positive if they are ADA negative or have missing data at baseline but develop an ADA response following study drug exposure (treatment-induced ADA response), or if they are ADA positive at baseline and the titer of one or more post-baseline samples is at least 0.60 titer units greater than the titer of the baseline sample (treatment-enhanced ADA response). Patients are considered to be ADA negative if they are ADA negative or have missing data at baseline and all post-baseline samples are negative, or if they are ADA positive at baseline but do not have any post-baseline samples with a titer that is at least 0.60 titer units greater than the titer of the baseline sample (treatment unaffected).

The relationship between [REDACTED] may be analyzed and reported descriptively via subgroup analyses.

4.8 BIOMARKER ANALYSES

[REDACTED]

[REDACTED]

The biomarker analyses will be reported separately from the CSR.

4.9 MISSING DATA

Please refer to Sections 4.4.1 and 4.4.2 for methods of handling missing data for the primary and secondary efficacy endpoints.

Any incomplete or missing death date will be handled separately for safety and efficacy analyses. In safety analyses, all deaths will be included, regardless of completeness of death date; patients who died with a partial or missing death date will be included as an event. In efficacy analyses, a death is considered an event only if a complete death date is available; patients who died with only a partial or missing death date will not be considered as a death event.

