6.4.2 Secondary Efficacy Endpoints

The secondary efficacy endpoints are listed in Section 2 (see [Table 1](#)).

PFS, as determined by an independent review committee according to RECIST v1.1, will be analyzed using the same methods described for PFS in Section [6.4.1](#).

Objective response will be presented as objective response rate (ORR), defined as the total number of patients whose objective response is CR or PR, divided by the number of patients in the ITT population. Objective response is defined as a CR or PR on two consecutive occasions ≥ 4 weeks apart, as determined by the investigators using RECIST v1.1. A 95% Clopper-Pearson CI will be calculated for the ORR.

For patients who achieve an objective response, DOR is defined as the time from the first occurrence of a documented objective response to disease progression, as determined by the investigator according to RECIST v1.1, or death from any cause, whichever occurs first. The censoring method for DOR will be the same as that for PFS. The Kaplan-Meier approach will be used to estimate median DOR. The 95% CI of the median DOR will be estimated using the Brookmeyer and Crowley method.

OS is defined as the time from randomization to death from any cause. For patients who are alive at the time of analysis data cut-off, OS time will be censored at the date the patient was last known to be alive. Survival time for patients with no post-baseline survival information will be censored at randomization. The Kaplan-Meier approach will be used to estimate median OS and 2-year landmark survival rate. The 95% CI of the median OS will be estimated using the Brookmeyer and Crowley method. The 95% CI of landmark survival rate will be calculated using the standard error derived from Greenwood's formula.

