2.2 ENDPOINTS

2.2.1 Primary Efficacy Endpoints

The primary efficacy endpoint is the investigator-assessed PFS per RECIST v1.1, defined as the time from randomization to the first occurrence of disease progression, as determined by an investigator according to RECIST v1.1, or death from any cause, whichever occurs first.

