2.2.2 Secondary Efficacy Endpoints

The secondary efficacy endpoints are as follows:

- IRC-assessed PFS per RECIST v1.1, defined as the time from randomization to the first occurrence of disease progression, as determined by the IRC according to RECIST v1.1, or death from any cause, whichever occurs first
- Overall survival (OS), defined as the time from randomization to death from any cause
- Objective response, defined as a complete response or a partial response on two consecutive occasions ≥ 4 weeks apart, as determined by the investigator according to RECIST v1.1

- Duration of response (DOR), defined as the time from the first occurrence of a documented objective response to disease progression, as determined by the investigator according to RECIST v1.1, or death from any cause, whichever occurs first
- Time to deterioration in global health status, defined as the time from randomization to first observed \geq 10-point decrease in European Organization for Research and Treatment of Cancer Core Quality of Life Questionnaire (EORTC QLQ-C30) linearly transformed global health status scale score that is sustained for two consecutive assessments or followed by death while the patient is on treatment
- Time to deterioration in physical functioning, defined as the time from randomization to first observed \geq 10-point decrease in EORTC QLQ-C30 linearly transformed physical functioning scale score that is sustained for two consecutive assessments or followed by death while the patient is on treatment

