4.4.1 Primary Efficacy Endpoint

The primary efficacy analysis will be the comparison of PFS, as determined by the investigator, between the two treatment arms using the stratified log-rank test at an overall 0.05 significance level (two-sided).

The statistical hypothesis of this study is as follows:

- H_0 : PFS (Arm A)=PFS (Arm B)
- H_1 : PFS (Arm A)≠PFS (Arm B)

PFS (Arm A) represents the survival function of PFS in the placebo+cobi+vem arm, and PFS (Arm B) represents the survival function of PFS in the atezo+cobi+vem arm.

PFS, as assessed by the investigator, is defined as the time from randomization to the first occurrence of disease progression, as determined by the investigator according to RECIST v1.1, or death from any cause, whichever occurs first. Data for patients who have not experienced disease progression or death at the time of analysis data cut-off will be censored at the date of last tumor assessment. Data for patients without post-baseline tumor assessment will be censored at randomization date.

The hazard ratio (HR) for PFS will be estimated using a stratified Cox model, and two-sided 95% CIs for the HR will be provided. Results from an unstratified analysis will

also be presented. Kaplan-Meier methodology will be used to estimate the median PFS for each treatment arm, and Kaplan-Meier curves will be produced. The 95% CI of the median PFS for each treatment arm will be constructed using the Brookmeyer and Crowley method ([Brookmeyer and Crowley 1982](#)).

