4.4.2.4 Overall Survival

OS is defined as the time from randomization to death from any cause. For patients who are alive at the time of analysis data cut-off, OS time will be censored at the date the patient was last known to be alive. Survival time for patients without post-baseline survival information will be censored at randomization date.

The OS will be compared between the two treatment arms using a two-sided stratified log-rank test at an overall two-sided 0.05 significance level. The HR for OS will be estimated using a stratified Cox model, and two-sided 95% CIs for the HR will be provided.

The OS will be compared between the two treatment arms at [REDACTED] interim analyses and [REDACTED] final analysis. [REDACTED]
[REDACTED]
[REDACTED]

To control the overall type I error rate at the 0.05 level (two sided), the secondary endpoint OS will be evaluated for statistical significance at the 5% level (two sided) only if the primary PFS endpoint meets statistical significance. The Lan–DeMets implementation ([Lan and DeMets 1983](#)) of the O’Brien–Fleming use function will be used to control the type I error at the 5% level (two-sided) for the OS evaluation in the interim and final analyses. See Section [4.10.2](#) for details.

Stratified analyses will incorporate the same stratification factors for the analysis of PFS.

Kaplan–Meier methodology will be used to [REDACTED]
[REDACTED]. The 95% CI of the [REDACTED] will be constructed using the Brookmeyer and Crowley method ([Brookmeyer and Crowley 1982](#)).

As a sensitivity analysis, an unstratified log–rank test will be performed and the unstratified HR will be provided.

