4.4.4 Exploratory

4.4.5 Sensitivity Analyses

4.4.5.1 Missing Tumor Assessment

The impact of missed scheduled tumor assessments on PFS will be assessed. If patients missed two or more consecutive assessments scheduled immediately prior to the date of disease progression per RECIST v1.1 or death, a sensitivity analysis will be performed where patients who missed two or more scheduled assessments immediately prior to the date of disease progression per RECIST v1.1 or death will be censored at date of the last tumor assessment prior to the missed visits, or at randomization date if no post-baseline tumor assessment prior to the missed visits.

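### SAP 4.9 turns a known death with an incomplete date into a non-event for OS and PFS, and no rule says where that patient is censored

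*SAP*

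**What the plan says.** SAP 2.2.2 gives "Overall survival (OS), defined as the time from randomization to death from any cause". The PFS definition in SAP 2.2.1 ends "or death from any cause, whichever occurs first". Neither depends on how complete the death date is.

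SAP 4.9 then separates safety from efficacy. For safety, all deaths count, whatever the state of the date. For efficacy, "patients who died with only a partial or missing death date will not be considered as a death event". On missing data generally, the section says "Please refer to Sections 4.4.1 and 4.4.2 for methods of handling missing data for the primary and secondary efficacy endpoints".

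The censoring rules in those sections are:

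- **OS (SAP 4.4.2.4):** "For patients who are alive at the time of analysis data cut-off, OS time will be censored" at the last date known alive. Patients with no post-baseline survival information are censored at randomization.
- **PFS (SAP 4.4.1):** "Data for patients who have not experienced disease progression or death at the time of analysis data cut-off will be censored" at the last tumor assessment, or at randomization if there is none.
- **Duration of response (SAP 4.4.2.3):** follows PFS.

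The sensitivity analyses in SAP 4.4.5 cover missed scans, non-protocol anti-cancer therapy and delayed treatment effect. None concerns undated deaths.

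**The concern.** A death known to the month and year would be a death in the safety tables and a non-event in the OS analysis. That contradicts the endpoint definitions. It also makes the censoring informative, because the patient leaves the risk set precisely because death occurred.

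The patient then has no assigned censoring date. The OS rule is limited to patients alive at cut-off, and the PFS rule to patients with neither progression nor death. Two analysts could choose different dates and obtain different OS curves.

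Most exposed are the descriptive OS estimates. Protocol 6.4.2 says the Kaplan-Meier approach "will be used to estimate median OS and 2-year landmark survival rate", and 2-year survival is a secondary endpoint in Protocol Table 1. OS is also formally tested after PFS (SAP 4.4.2.4), so a difference between arms in the share of incomplete dates would carry into a tested hazard ratio.

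**Working it through.** **No plan figure to reproduce.** The event counts, medians, hazard ratios and power are redacted, and the share of incomplete death dates is not given. From the documents: about 500 patients, 1:1, two-sided 0.05, and survival contact about every 12 weeks (Protocol 4.6.2). Everything else below is assumed.

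**1. Which rule applies?** Take a patient who died without recorded progression and whose death date is partial.

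- Not an OS or PFS event, by SAP 4.9.
- Not alive at cut-off, so outside the OS censoring rule.
- Has died, so outside the literal PFS censoring rule.
- Normally has post-baseline survival information, so outside the randomization rule for OS.

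The steps below use the natural but unwritten reading: last date known alive for OS, last tumor assessment for PFS.

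**2. Size for OS, analytic.** If a share f of deaths becomes censored, the hazard is multiplied by about (1 − f). With exponential OS and a median of 25 months, S(24) = 0.5^(24/25) = 51.4%. Under the rule it becomes 0.5^(24(1 − f)/25):

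- f = 2%: 52.1% (+0.69 points)
- f = 5%: 53.1% (+1.74)
- f = 10%: 54.9% (+3.54)

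**3. Size for OS, simulated.** Settings: 250 per arm, control median 25 months, HR 0.80, 15-month uniform accrual, cut-off at 60 months, last date known alive 0–12 weeks before death, 1,500 replicates per row. In each pair the first figure counts all deaths and the second applies SAP 4.9.

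| Incomplete, both arms | Control 2-year survival, % | Gain, control / atezolizumab | Control median, months | Deaths counted | HR |
|---|---|---|---|---|---|
| 2% | 51.3 → 52.0 | 0.7 / 0.6 | 24.8 → 25.4 | 363 → 356 | 0.798 → 0.798 |
| 5% | 51.5 → 53.2 | 1.7 / 1.6 | 24.9 → 26.4 | 363 → 345 | 0.801 → 0.802 |
| 10% | 51.4 → 54.8 | 3.4 / 3.1 | 24.9 → 27.8 | 363 → 326 | 0.796 → 0.795 |

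With control medians of 20 and 30 months, the control gains are 0.7/1.7/3.6 and 0.7/1.6/3.2 points. Across all nine settings the HR moves by at most 0.003.

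**4. Unequal shares.** The HR is multiplied by about (1 − f_B)/(1 − f_A). With a true HR of 0.80:

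- 3% in Arm A and 5% in Arm B: 0.80 × 0.95/0.97 = 0.78
- 5% in Arm A and 3% in Arm B: 0.80 × 0.97/0.95 = 0.82

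A one-point difference therefore changes the HR by about 1%. With a true HR of 1, a single two-sided test on D deaths has shift |ln HR| × √(D(1 − f̄)/4), where f̄ is the mean share. For 200–350 deaths, 1% versus 5% gives an apparent HR of 0.96 and rejection in 6.0–6.7% of trials; 0% versus 5% gives 0.95 and 6.5–7.6%.

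**5. PFS.** Only deaths without earlier progression are lost. If 10–20% of events are such deaths and 5% of their dates are incomplete, the loss is 0.10 × 0.05 = 0.5% to 0.20 × 0.05 = 1% of events, or 1.5–3 per 300. A median of 11–14 months (the range in Protocol 1.1) moves by 11/0.995 − 11 = 0.06 to 14/0.99 − 14 = 0.14 months.

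**6. Does imputation repair it?** In the 5% case of step 3, bounded midpoint imputation gives control 2-year survival of 51.47% against 51.5%. A harder assumed case has 5% of deaths undated, last contact up to 24 months before death, the report up to 6 months after, and 2,000 replicates:

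| Rule | Control 2-year survival, % | Error, points |
|---|---|---|
| Truth | 51.37 | – |
| SAP 4.9 | 52.64 | +1.27 |
| Bounded midpoint | 51.07 | −0.30 |
| All at lower bound | 50.65 | −0.72 |
| All at upper bound | 51.59 | +0.22 |

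The HR is 0.80 under every rule.

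**The case against.** The strongest reply is that little is at stake. Death reporting forms and data queries (Protocol 5.3.5.8, 5.6, 7.1) and 12-weekly contact should keep incomplete dates rare. At 2%, the 0.7-point gain is about a fifth of the standard error of 2-year survival, √(0.514 × 0.486/250) = 3.2 points. The trial is double-blind with the same survival follow-up in both arms, so a large imbalance in incomplete dates is unlikely. For PFS, an undated death counted as no event falls naturally to the last tumor assessment. Public records used to trace withdrawn patients may well hold full dates. All of this stands as a limit on size. It does not remove the contradiction with the endpoint definitions or supply the missing OS censoring date.

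A second reply is that imputation puts assumed event times into the main analysis and, for PFS, counts deaths long after the last scan. The PFS part fails: SAP 4.4.1 already counts a fully dated death however long after the last scan, and leaves the matter to a sensitivity analysis ("The impact of missed scheduled tumor assessments on PFS will be assessed"). The imputation error is real but bounded, and smaller than the bias of the current rule in the hard case above.

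A third reply concerns timing. The SAP carries the Version 4 synopsis, while Protocol Version 9 (Section 1.3) already describes approval of the triple combination. If OS results by arm are already known, changing the main rule would be post hoc. That is a fair caution about how the change is made.

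**Conclusion.** The point holds and should be fixed. SAP 4.9 departs from the endpoint definitions, and the censoring date for these patients is not written; neither statement rests on an assumed number. The size does. Under the natural reading and exponential OS with a control median of 20–30 months, 2-year survival is overstated by about 0.7 points per arm at 2% incomplete dates, 1.6–1.7 at 5% and 3.2–3.6 at 10% (control arm). The hazard ratio is essentially unbiased when the shares are equal and shifts by about 1% per one-point difference between arms. The effect on the primary endpoint is small.

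**What to change.** Replace the efficacy part of SAP 4.9 with a rule along these lines:

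- Every death known to have occurred by the data cut-off is an event for OS and, where there is no earlier progression, for PFS.
- **Partial date:** impute the midpoint of the dates compatible with the known parts, no earlier than the day after the last date known alive and no later than the earlier of the report date and the cut-off.
- **Wholly missing date:** impute the midpoint between those same two bounds.
- Repeat OS and 2-year survival with all such deaths at the lower bound and again at the upper bound, and report the number of imputed dates by arm.
- Keep the current rule as a sensitivity analysis, stating its censoring dates for OS and PFS.

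The cost is one paragraph and a short derivation, fixed before unblinding. If any OS result by arm has already been seen, the amendment should say so and both sets of results should be reported. The imputation error is small for partial dates and larger for wholly missing dates in withdrawn patients, which is what the two bound analyses are there to show.
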